11.6 Pregnancy

Any pregnancy that occurs during study participation must be reported. To ensure subject safety, each pregnancy must be reported to the FDA with CC notification to INCYTE [contact] within 2 weeks of learning of its occurrence. The pregnancy must be followed up to determine outcome (including premature termination) and status of mother and child. Pregnancy complications and elective terminations for medical reasons must be reported as an AE or SAE. Spontaneous abortions must be reported as an SAE. Any SAE occurring in association with a pregnancy, brought to the investigator's attention after the subject has completed the study and considered by the investigator as possibly related to the investigational product, must be promptly reported to the pharmacovigiliance group at the H. Lee Moffitt Cancer Center. In addition, the investigator must attempt to collect pregnancy information on any female partners of male study subjects who become pregnant while the subject is enrolled in the study. Pregnancy information must be reported to the H. Lee Moffitt Cancer Center as described above.

11.7 Time Period and Frequency of Detecting AEs and SAEs

The investigator or site staff is responsible for detecting, documenting and reporting events that meet the definition of an AE or SAE. AEs will be collected from the start of Investigational Product and through the follow-up contact. SAEs will be collected over the same time period as stated above for AEs. However, any SAEs assessed **as related** to study participation (e.g., investigational product, protocol mandated procedures, invasive tests, or change in existing therapy) will be recorded from the time a subject consents to participate in the study up to and including any follow-up

contact. All SAEs will be reported to INCYTE [contact] within 24 hours, as indicated.

11.8 Prompt Reporting of Serious Adverse Events and Other Events to the FDA with notification to INCYTE

Any serious adverse events which occur during the clinical study or within 30 days of receiving the last dose of study medication, whether or not related to the study drug, must be reported by the investigator. In addition, any SAEs which occur as a result of protocol specific diagnostic procedures or interventions must also be reported. SAEs brought to the attention of the investigator at any time after cessation of ruxolitinib and considered by the investigator to be related or possibly related to ruxolitinib must be reported to FDA with notification to INCYTE [contact] if and when they occur. Additionally, in order to fulfill international reporting obligations, SAEs that are related to study participation (e.g., procedures, invasive tests, change from existing therapy) or are related to a concurrent medication will be collected and recorded from the time the subject consents to participate in the study until he/she is discharged.

	In	itial Reports		nformation on a ous Report
Type of Event	Time	Documents	Time Frame	Documents
	Frame			
All SAEs	24 hours*	"SAE" data collection	24 hours*	Updated "SAE"
		tool		data collection tool
Pregnancy	2 Weeks*	Pregnancy	2 Weeks*	Pregnancy Follow-
		Notification Form		up Form

• From the time point when the SAE or pregnancy became known to reporter.

11.9 Regulatory Reporting Requirements for SAEs

Prompt notification of SAEs by the investigator to the FDA (and INCYTE [contact]) is essential so that legal obligations and ethical responsibilities towards the safety of subjects are met. The sponsor-investigator has a legal responsibility to notify both the local regulatory authority and other regulatory agencies about the safety of a product under clinical investigation. The sponsor-investigator will comply with specific regulatory requirements relating to safety

reporting to the regulatory authority, /Institutional Review Board (IRB), the FDA, notification to INCYTE, and sub-investigators. Investigator safety reports are prepared for suspected unexpected serious adverse reactions according to local regulatory requirements and those policies set forth by the FDA and are forwarded to investigators and INCYTE as necessary. An investigator who receives an investigator safety report describing an SAE(s) or other specific safety information (e.g., summary or listing of SAEs) from the H. Lee Moffitt Cancer Center will file it with the CIB and will notify the IEC /IRB, if appropriate according to local requirements.

12 PHARMACEUTICAL INFORMATION

12.1 Packaging and Labeling

Ruxolitinib 5 mg tablets are packaged as 60 count in high-density polyethylene (HDPE) bottles. The bottles will include labeling "New Drug - Limited by Federal (USA) Law to Investigational Use.

12.2 Preparation

Tablets will be provided to the site and no specific preparation of study medication is required prior to administration.

12.3 Handling and Storage

Investigational product must be dispensed or administered according to procedures described herein. Only subjects enrolled in the study may receive investigational product, in accordance with all applicable regulatory requirements. Only authorized site staff may supply or administer investigational product. All investigational products must be stored in a secure area with access limited to the investigator and authorized site staff and under physical conditions that are consistent with investigational product-specific requirements. The bottles of tablets should be stored at room temperature, 15°C to 30°C (59°F to 86°F). Any unused investigational product will be returned to INCYTE for destruction or destroyed at the institution per institutional policy (if allowable).

13 Study Calendar

All screening evaluations will be performed within 4 weeks prior to the start of ruxolitinib treatment. Subjects must have a bone marrow biopsy and aspirate (including

cytogenetics) performed within 4 weeks prior to the start of treatment. All transfusion and pre-transfusion Hgb or platelet count must be recorded for the 8 weeks prior to initiation of study treatment. Strict adherence to the visit schedule is required. In the event that a visit or test cannot be scheduled on the exact visit day, a window of \pm 7 days is allowable. Bone marrow aspiration and biopsy exams can be done within a 14 day window of the allotted date. Tests (including bone marrow biopsies and aspirates) done within the screening period prior to signing informed consent are allowed for use in this study.

- 13.1 **Baseline Assessment**: within 4 weeks of starting treatment Medical history including:
 - disease characteristics such as first diagnosis of CMML, WHO/FAB subtype, IPSS score, MD Anderson Scoring System (MDASC), prior treatments.
 - ECOG performance status.
 - Concurrent medication review.
 - red blood cell and platelets transfusion past 8 weeks if available.
 - Routine physical examination to include vital signs, height and weight.
 - Bone marrow examination, including cytomorphology, cytogenetic assessment, and flow cytometry analysis.
 - Laboratory assessments:
 - Hematology to include platelet count, hemoglobin, hematocrit, white blood cells
 (WBC) and WBC differential (including: neutrophils, eosinophils, basophils,
 lymphocytes and monocytes), INR, PT, and PTT and reticulocyte count.
 - Clinical chemistries including BUN/urea, creatinine, sodium, potassium,
 alkaline phosphatase, alanine aminotransferase (ALT), aspartateaminotransferase
 (AST), , total bilirubin, bicarbonate, calcium, chloride, glucose, LDH, total protein,
 albumin.
 - Urine or serum pregnancy test for females of childbearing potential will be performed at Screening or on Day 1, prior to first dose of study medication.
 Symptom Score using the The Myeloproliferative Neoplasms Symptom Assessment
 - Form (MPN-SAF). (see Appendix D)

Review and record any blood and blood supportive care products for the prior 8 weeks.

- 13.2 Treatment Period (weeks 1-16): Ruxolitinib will be administered as a twice daily oral dose for a 4-week treatment cycle. Subjects will have a CBC with leukocyte differential performed weekly; a blood chemistry will be performed weekly for first cycle and then q 2 weeks. A BM aspirate and biopsy with cytogenetic analysis will be performed after cycle 2 and 4 (weeks 8, 16) to assess pathologic response, cytogenetic response and disease progression. For subjects who achieve CR, marrow CR, or PR a confirmation bone marrow aspirate and biopsy should be obtained 4 to 8 weeks after documentation of CR, marrow CR, or PR.
- 13.3 Week 16 End of Treatment: Subjects will complete a response assessment within one week after their last administration of ruxolitinib. Subjects discontinuing study early should complete their end of treatment visit within two weeks after their last dose of investigational product. Physical exam, vital signs, concomitant medication, adverse event reporting, CBC, and blood chemistry and BM aspirate and biopsy with cytogenetic analysis will be performed.
- Continuation Phase: After completing cycle 4 response assessments, responders may continue to receive ruxolitinib and the final week 16 dose in the absence of DLT or disease progression until marketing approval of ruxolitinib for CMML. Bone marrow biopsy and aspirate will be repeated after every 4 cycles (For subjects who achieve CR, marrow CR, or PR a confirmation bone marrow aspirate and biopsy should be obtained 4 to 8 weeks after documentation of CR, marrow CR, or PR). A CBC will be obtained and complete metabolic profile as per standard of care. The off treatment assessment should be done within a week off treatment.
- 13.5 Off Treatment assessment: includes best response achieved, date of first response, date of loss of response, reason for discontinuation.
- 13.6 **Off study evaluation**: include vital status, date of death/last contact, transformation to AML and the date of transformation to AML if applicable. This evaluation will be updated every 6 month for 2 years.

Study Calendar	Pre- Study	Wk 1	Wk 2	Wk 3	Wk 4	Wk 5	Wk 6	Wk 7	Wk 8	Wk 9	Wk 10	Wk 11	Wk 12	Wk 13	Wk 14	Wk 15	Wk 16	Wk 17	Weeks 18-48 (if response) Monthly visits	Off-Study or continue if responding as per previous weeks
Ruxolitiniba		X	X	X	X	X	X	X	X	X	X	X	X	X	X	X	X	X	X	X
Informed consent	X		1																	
Demographics	X				71											L				
Medical history	X					X				X				X				X	X	X
Physical exam	X					X				X				X				X	X	X
Vital signs	X					X				X				X				X	X	X
Height	X																			X
Weight	X					X				X				X				X	X	
Performance Status	X					X		N.		X				X				X	X	X
Concurrent medication review	X								М											
CBC w/diff,	X	X	X	X	X	X	X	X	X	X	X	X	X	X	X	X	X	X	X	X
Retic Count	X					X				X				X				X		
Serum chemistry ^b	X	X	X	X	X		X		X		X		X		X		X		X	X
INR, PT, and PTT	X							1		7						7				
Adverse event evaluation		X				events v								-						
Bone marrow biopsy/aspirate ^d ***	X			١,					X	•			Ĭ				X			
B-HCG ^c	X				4															
Lab. Correlates	X	X				X				X				X				X		

Prior CMML	X																			
Treatments																				
Transfusion	X					X				X				X				X	X	X
Log																				
Response										X								X	X	X
Assessments															_					
Symptom Score Scale ^f	X	X	X	X	X	X	X	X	X	X	X	X	X	X	X	X	X	X		
Scale ^f																				
Off-treatment																		X	X	X
Assessment/Off																				
-Study Follow-					7															
-Study Follow- up/ CMML Summary Form																				
Summary Form																				

- a. Dose as assigned for cohort in phase 1, dose assigned as MTD in phase 2
- b: Albumin, alkaline phosphatase, total bilirubin, bicarbonate, BUN, calcium, chloride, creatinine, glucose, LDH, potassium, total protein, AST, ALT, sodium, and total bilirubin.
- c: Serum or urine pregnancy test (women of childbearing potential).
- d: in addition to specimen required for pathologic review, and additional aspirate will be collected (goal volume of 30cc)
- e: in addition to specimen required for routine labs, 6 green top vials, 1 red top vial; on week 1, peripheral blood will be collected twice: at time of first dose, and 3 hours after first dose.
- f: The Myeloproliferative Neoplasms Symptom Assessment Form (MPN-SAF) using ERT's DiaryPro done by the patient. Data upload and device maintenance will occur at each scheduled visit.

Week 16 Evaluation and End of Treatment: Subjects will complete a response assessment within one week after their last administration of ruxolitinib. Subjects discontinuing study early should complete their end of treatment visit within two weeks after their last dose of investigational product. Physical exam, vital signs, concomitant medication, adverse event reporting, CBC, and blood chemistry and BM aspirate and biopsy with cytogenetic analysis will be performed.

- **Continuation Phase: After completing cycle 4 response assessments, HI-platelet responders may continue to receive ruxolitinib and the final week 16 dose in the absence of DLT or disease progression until marketing approval of ruxolitinib for CMML. Bone marrow biopsy and aspirate will be repeated after every 4 cycles. A CBC will be obtained and complete metabolic profile as per standard of care. The off treatment assessment should be done within a week off treatment.
- *** For subjects who achieve CR, marrow CR, or PR a confirmation bone marrow aspirate and biopsy should be obtained 4 to 8 weeks after documentation of CR, marrow CR, or PR.
- Off Treatment assessment: includes best response, date of first response, date of loss of response, reason for discontinuation.

Off study follow up: include vital status, date of death/last contact, transformation to AML and the date of transformation to AML if applicable. This evaluation will be updated every 6 month for 2 years.

**** all dates are +/- one week

14 MEASUREMENT OF EFFECT

Definitions:

Response and progression will be assessed according to modified International Working Group (IWG) 2006 criteria²³(Appendix B). Improvements must last ≥ 8 weeks.

• Erythroid Response for pretreatment hemoglobin < 11 g/dl:

 \geq 1.5 g/dL increase in hemoglobin.

For transfused subjects having pre-transfusion baseline hemoglobin ≤ 9 g/dL, a reduction of 4 or more RBC units in the previous 8 weeks compared with pretreatment.

 \circ Platelet response for subjects with a pre-treatment platelet count $< 50 \times 10^9 / L$:

Major platelet response: An absolute increase of $\geq 30 \times 10^9$ /L. If platelets are $< 20 \times 10^9$ /L at baseline, then a 100% increase will qualify as a major platelet response. If subjects are transfusion dependent at baseline, platelet transfusion independence sustained for 8 consecutive weeks will qualify as a major platelet response.

Complete platelet response: increase of platelet count to $\geq 100 \times 10^9/L$ for 8 consecutive weeks.

• Neutrophil response with pretreatment ANC $< 1 \times 10^9$ /L:

 \geq 100% increase and an absolute increase of \geq 0.5 x 10⁹/L

Progression/relapse following hematological improvement: At least one of the following:

Any newly developed (RBC/platelet) transfusion dependence,

 \geq 50% decrease from maximum response levels in granulocytes or platelets, or

Reduction of ≥ 1.5 g/dL hemoglobin.

Complete Response (CR)

Bone marrow: \leq 5% myeloblasts with normal maturation of all cell lines Persistent dysplasia will be noted

Peripheral blood:

Hemoglobin $\geq 11 \text{ g/dL}$

Platelets $> 100 \times 10^9 / L$

Neutrophils $\geq 1.0 \times 10^9/L$

BLASTS < 0%

o Partial Response (PR)

All CR criteria if abnormal before treatment, except:

Bone marrow blasts decreased by $\geq 50\%$ over pretreatment but still $\geq 5\%$

Cellularity and morphology not relevant

Marrow Complete Response (mCR)

Bone marrow: $\leq 5\%$ myeloblasts and decrease by $\geq 50\%$ over pretreatment **Peripheral blood: if HI responses, they will be noted in addition to marrow CR**

Stable Disease (SD)
 Failure to achieve at least PR, but no evidence of progression for > 8 weeks
 Duration of Response:

The duration of response is measured from the time measurement criteria are met for major or complete platelet response (which ever is first recorded) until the first date that disease progression defined by the bone marrow response outlined above, progression/relapse following a CR, marrow CR or PR, or progressions/relapse following hematological improvement (HI) as outlined above.

Pathologic Response: Pathologic response is categorized as a CR, mCR or a PR. Response parameters in the peripheral blood and/or bone marrow must be sustained for at least 4 weeks. See appendix B.

Symptom Assessment in CMML

Symptoms of CMML will be assessed using the MPN-SAF (see Appendix D). Subjects will be issued a hand-held device (eDiary) on which to record symptoms of CMML. The subject will be instructed to complete the eDiary each night beginning on Day -4 or earlier of the screening phase (eg, 4 days prior to Cycle 1 Day 1) through treatment discontinuation. Subjects will bring the device to the study site at each study visit so that the device charging can be verified and accumulated data can be downloaded, as applicable. The device will then be returned to the subject at these same visits for continued use each night. The subject will return the device and the docking station for the final time at the EOT visit so that the data can be archived. Detailed directions for the administration of the eDiary will be provided in the Study Reference Manual.

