3 STUDY ENDPOINTS

3.1 Primary

- 3.1.1 The maximum tolerated dose (MTD) of ruxolitinib for the treatment of CMML. The MTD is defined as the highest dose where less than 33% of subjects experience a drug related predefined dose limited toxicity (DLT).
- 3.1.2 Proportion of subject achieving clinical benefit defined as hematologic improvement, complete remission, partial remission, or stable disease by the IWG 2006 criteria (see appendix B)

- 3.2 Secondary
- **3.2.1** Acute myeloid leukemia (AML) transformation according to WHO criteria.
- **3.2.2** Overall survival (OS).
- **3.2.3** Duration of response.
- 3.2.4 The Myeloproliferative Neoplasms Symptom Assessment Form (MPN-SAF) at baseline and at best response.
- 3.2.5 >50% decrease in splenic length as measured by physical exam if applicable
- **3.2.6** The suppression of pSTAT5 intracellular signaling after ruxolitinib in CMML subjects (pretreatment, at 1-2hr post treatment, cycle 2, cycle 4, and progression.)
- **3.2.7** Determine number of colonies formed in the presence of GM-CSF and/or ruxolitinib (pretreatment and progression) as a future predictor of response.
- 3.2.8 Mutational status in our CMML subjects by sanger sequencing of JAK2, c-CBL, N-RAS, K-RAS,RUNX-1, TET2, SRSF2, EZH2, ASXL1, and DNMT3a (pretreatment and progression).
- 3.2.9 Mutational status of JAK2 tyrosine kinase at time of progression by deep sequencing of JAK2 to include M929I, Y931C, G935R, R938L, I960V, E985K. (pretreatment and at progression)

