4.2 Exclusion Criteria

- 4.2.1 Any of the following lab abnormalities:
- 4.2.1.1 Platelet count of less than 35,000/uL
- 4.2.1.2 Absolute Neutrophil Count (ANC) of less than 250 cells/uL
- 4.2.1.3 Serum Creatinine \geq 2.0
- 4.2.1.4 Serum total bilirubin >1.5 x ULN
- 4.2.2 Use of cytotoxic chemotherapeutic agents, or experimental agents (agents that are not commercially available) for the treatment of CMML within 28 days of the first day of study drug treatment.
- 4.2.3 Any serious medical condition or psychiatric illness that will prevent the subject from signing the informed consent form or will place the subject at unacceptable risk if he/she participates in the study.
- 4.2.4 Concurrent use of GM-CSF. G-CSF could be used for the short-term management of neutropenic infection. Stable doses of erythropoietin stimulating agents that were started >8 weeks from first ruxolitinib dose or corticosteroids that were being administered prior to screening are allowed.
- 4.2.5 Uncontrolled current illness including, but not limited to ongoing or active infection, symptomatic congestive heart failure, unstable angina pectoris, cardiac arrhythmia, or psychiatric illness/social situations that would limit compliance with study requirements.
- 4.2.6 History of metastatic malignancy in the preceding 2 years.
- 4.2.7 Pregnant women are excluded from this study because ruxolitinib has not been studied in pregnant subjects. Because there is an unknown but potential risk for

adverse events in nursing infants secondary to treatment of the mother with ruxolitinib, breastfeeding should be discontinued if the mother is treated with ruxolitinib.

4.2.8 Patients who have participated in other interventional (treatment-related) clinical trials within 30 days of enrollment are excluded.

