District magnency (III D)	9.0 g/dL pretreatment will count in the RBC transfusion evaluation Platelet response (HI-P) Absolute increase of $\geq 30 \times 10^9$ /L for subjects starting with $\geq 20 \times 10^9$ /L						
Platelet response (HI-P) (Pretreatment < 100 x 10 ⁹ /L)	Absolute increase of $\ge 30 \times 10^{7}$ L for subjects starting with $\ge 20 \times 10^{7}$ L Increase from $< 20 \times 10^{9}$ /L to $\ge 20 \times 10^{9}$ /L and by at least 100%						
	At least 100% increase and an absolute increase of > 0.5 x 10 ⁹ /L						
Neutrophil response (HI-N)	At least 100% increase and an absolute increase of > 0.5 x 10 /L						
(Pretreatment $< 1.0 \times 10^9/L$)							

PROGRESSION/RELAPSE CRITERIA FOR SUBJECTS WITH CMML

ALTERING DISEASE NAT	URAL HISTORY					
Disease Progression (PD)	For subjects with:					
	Less than 5% blasts: \geq 50% increase in blasts to $>$					
	5% blasts					
	5%-10% blasts: \geq 50% increase in blasts to \geq 10%					
	blasts					
	10%-20% blasts: \geq 50% increase in blasts to \geq 20%					
	blasts					
	20%-30% blasts: \geq 50% increase in blasts to \geq 30%					
	blasts					
	Any of the following:					
	At least 50% decrement from maximum					
	remission/response levels in granulocytes or					
	platelets					
	Reduction in hemoglobin (Hgb) concentration by ≥					
	2 g/dL					
Disease transformation	Transfusion dependence					
	Transformation to AML (30% or more blasts)					
Relapse after CR or PR	At least one of the following:					
	Return to pretreatment bone marrow blast % Decrement of ≥ 50% from maximum					
	remission/response levels in granulocytes or					
	platelets					
	- Reduction in Hgb concentration by ≥ 1.5 g/dL or transfusion					
	dependence					
HEMATOLOGICAL IMPR						
Progression/relapse after HI	At least one of the following:					
	At least 50% decrement from maximum response					
	levels in granulocytes or platelets					
	Reduction in Hgb by $\geq 1.5 \text{ g/dL}$					
	- Transfusion dependence					

21 APPENDIX C: CYP3A4 Strong Inhibitors

HIV Antivirals:

- -indinavir
- -boceprevir
- -lopinavir/ritonavir
- -ritonavir
- -telaprevir
- -nelfinavir
- -saquinavir

Others:

- -clarithromycin
- -conivaptan
- -grapefruit juice
- -mibefradil
- -posaconazole
- -voriconazole
- -itraconazole
- -ketoconazole
- -nefazodone
- -telithromycin

^{*} Dose reductions as in section 7 are required for strong inhibitors of the CYP3A4.

22 APPENDIX D: Myeloproliferative Neoplasms-Symptom Assesment Form (MPN-SAF)

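### Section 14 and Appendix B set different baseline platelet limits (50 and 100 x10^9/L) for the same platelet improvement, so subjects starting at 50 to <100 are classified differently

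*Combined protocol and SAP*

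**What the plan says.** Section 14 opens with "Response and progression will be assessed according to modified International Working Group (IWG) 2006 criteria" and points to Appendix B. It then gives "Platelet response for subjects with a pre-treatment platelet count" below 50 x10^9/L. Two categories sit under that limit:

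- a major response ("Major platelet response: An absolute increase of" at least 30 x10^9/L, with separate branches for baselines below 20 and for transfusion-dependent subjects);
- a complete response, meaning a count of at least 100 x10^9/L held for 8 consecutive weeks, with no minimum rise.

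Section 14 requires improvements to last at least 8 weeks.

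Appendix B heads HI-P with "Pretreatment < 100 x 10"^9/L and asks for the same absolute rise of at least 30 x10^9/L from a baseline of 20 or more. It also has a branch for baselines below 20, and it has no complete platelet response.

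The phase 2 primary endpoint in Section 3.1.2 is "Proportion of subject achieving clinical benefit defined as hematologic improvement, complete remission, partial remission, or stable disease by the IWG 2006 criteria", with a reference to Appendix B alone. Section 4.2.1.1 excludes "Platelet count of less than 35,000/uL".

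Three other places use the platelet categories. Section 14 starts duration of response at major or complete platelet response. Section 15.5 summarises complete platelet response. The Continuation Phase note under the study calendar refers to responders on platelet improvement, where the Continuation Phase paragraph in the body of Section 13 refers to responders in general.

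**The concern.** Two parts of one document give different entry conditions for the same improvement, and the one with the narrower limit cites the other as its source. The difference falls on eligible subjects starting at 50 to <100 x10^9/L. Depending on the page used, such a subject is an HI-P responder with a response start date, or has no platelet response and no start date.

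Hematologic improvement is a component of the primary endpoint, and the phase 2 decision turns on small counts: stop at 1 or fewer of 10, reject the drug at 5 or fewer of 29. If the limit remains unsettled, it could be chosen after the platelet data are known, in a single-arm trial where one response can cross a boundary. Whether that happens depends on the role of stable disease, so that has to be worked through before any effect on the decision is claimed.

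**Working it through.** **1. The stated design, reproduced.** Section 15.2 gives rates of 10% and 30%, the rules 1/10 and 5/29, type I error 0.05, type II error 0.19 and early termination probability 0.74 under the null. Write b(n, x, p) for the binomial probability.

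- P(stop early) = b(10, 0, p) + b(10, 1, p). At p = 0.10 this is 0.3487 + 0.3874 = 0.736.
- P(declare active) = sum over x = 2 to 10 of b(10, x, p) × P(Bin(19, p) ≥ max(0, 6 − x)). At p = 0.10 this is 0.0471. At p = 0.30 it is 0.8051, so the type II error is 0.1949.

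All three agree with the plan at two decimals. The design arithmetic is not in question.

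**2. Both platelet rules applied to example subjects** (x10^9/L, rise held for 8 weeks):

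| Baseline → on treatment | Rise | Section 14 major response | Appendix B HI-P |
|---|---|---|---|
| 40 → 72 | 32 | yes | yes |
| 49 → 80 | 31 | yes | yes |
| 50 → 82 | 32 | no | yes |
| 60 → 92 | 32 | no | yes |
| 80 → 112 | 32 | no | yes |
| 99 → 130 | 31 | no | yes |

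For eligible subjects, the baselines open to platelet response are 35 to <50 under Section 14 and 35 to <100 under Appendix B. Subjects at 80 → 112 and 99 → 130 also pass 100, yet are not complete platelet responders in Section 14 because of the baseline limit.

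**3. Does the primary-endpoint count change?** Stable disease is less than partial remission with no progression for more than 8 weeks. Take a subject at 70 → 130.

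- Without progression: HI-P under Appendix B; stable disease if the Section 14 limit is used. Both count under Section 3.1.2. The label changes and the count does not.
- With progression on another ground: Appendix B lists, for example, a hemoglobin fall of at least 2 g/dL, transfusion dependence or a rise in blasts. The subject can be HI-P under Appendix B and neither HI nor stable disease under the Section 14 limit. The count changes. Section 2.3 reports more anemia and red-cell transfusion with ruxolitinib, so the case is plausible.
- If stable disease is not a response in Section 15.2: the count changes for any such subject who has no other response.

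**4. Illustration for the case where stable disease is excluded.** The documents give neither the share of subjects starting at 50 to <100 (s) nor the rate of qualifying rises among those with no other response (q). Assume s = 20% to 40% and q = 5% to 20%, with a true rate of 10% under the Section 14 limit. The rate under Appendix B is then 0.10 + s × q × 0.90.

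- Low end: 0.10 + 0.20 × 0.05 × 0.90 = 0.109; P(declare active) = 0.066.
- High end: 0.10 + 0.40 × 0.20 × 0.90 = 0.172; P(declare active) = 0.299.

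The comparison value is 0.047. These figures follow from the assumed ranges and are not estimates for this trial.

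**The case against.** The strongest answer is that the primary endpoint as written absorbs the difference. Section 3.1.2 and the synopsis both count stable disease, so a subject with a sustained rise and no progression is a success on either page. This stands. A reader might infer that the same platelet rise is a primary-endpoint success under one text and a failure under the other, and hence that the go/no-go count depends on the page used. The documents do not support that without one of the two conditions in step 3 of the working.

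Second, Section 3.1.2 refers to Appendix B alone, so someone scoring the primary endpoint has a named source. That also stands in large part. It does not cover duration of response or the Section 15.5 summary, which use categories defined only in Section 14.

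Third, Section 14 calls its criteria modified, so the limit of 50 might be deliberate. But the same sentence cites Appendix B, where the limit is 100, and nothing identifies the limit of 50 as the modification.

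Fourth, a reader might take the widths of the two baseline windows (15 of 65 units, 23%) as the share of subjects affected. It is a ratio of platelet-scale ranges and says nothing about how many subjects fall in each.

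**Conclusion.** The contradiction is real. For eligible subjects starting at 50 to <100 x10^9/L it changes the HI component of the primary endpoint and whether the duration-of-response clock starts, and these effects do not depend on how stable disease is treated.

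An effect on the 1/10 and 5/29 decisions is conditional. It needs either a reading of Section 15.2 that excludes stable disease or a platelet responder who does not qualify as stable disease. Section 15.2 tests a response rate, and the primary objective in Section 1.1.2 speaks of response rates, while Section 3.1.2 includes stable disease. The plan does not settle which applies. The number of subjects in the band is not given, so the size is unknown, and the range of 0.066 to 0.299 holds only under the stated assumptions.

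A reader might also conclude that the branch for baselines below 20 is dead text because entry requires 35. That goes too far. The plan does not say which count is the pre-treatment value when screening may precede treatment by up to 4 weeks, and Section 15.5 analyses treated subjects regardless of eligibility. This should be fixed, but it does not undermine the design.

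**What to change.** - State that HI-P for the primary endpoint is scored from Appendix B (baseline below 100 x10^9/L, rise of at least 30 x10^9/L) with the Section 14 duration of at least 8 weeks. Align the Section 14 limit for that rise.
- Keep the branch for baselines below 20 the same in both places. Removing it from Section 14 alone would create a new mismatch.
- Do not move the whole Section 14 platelet heading to 100. Complete platelet response has no minimum rise, so a sustained change from 95 to 100, a rise of 5, would qualify and enter the Section 15.5 summary. Either require the rise of at least 30 x10^9/L for the 50 to <100 band, or replace complete platelet response with HI-P in Section 15.5 and use HI-P in place of major or complete platelet response in the duration-of-response definition.
- State in Section 15.2 whether stable disease counts as a response.
- Reconcile the two Continuation Phase texts in Section 13, which describe the continuing group differently.

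The cost is a text amendment and re-scoring from the blood counts already scheduled. No procedure is added. The limit and the role of stable disease should be fixed without reference to response data.
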